## **Data Analysis**

By recruiting participants that have already been identified as being SARS-CoV-2/COVID-19 positive, we expect that approximately of 10% of individuals from each age group will eventually develop severe or critical COVID-19 symptoms and require hospitalization or treatment in an intensive care unit. Currently there are not sufficiently rigorous statistical models for predicting statistical power for machine learning studies. Some of the issues related to sample size for machine learning models have been recently reviewed in the scientific literature. Machine learning models can be trained to find an effect, but it is not clear if the effect is the result of over-fitting and/or poor sample selection. Nested crossvalidation and calibration have been proposed to mitigate these issues. Based on extensive prior experience of our group, we expect that 100 events in continuously monitored participants will be sufficient to assess the training performance of the model for early identification of novel digital biomarkers indicative of disease severity as well future trajectory of the severity of disease. Using the 100 events and approximate 10% event rate, testing and training cohorts of 1,000 participants (2,000 participants total) were determined.

Although not required in observational clinical trials due to no directly measured effect size, sample size calculations were conducted under different circumstances to ensure sample is sufficiently large for a clinical prediction model.

## **Substudy**

### **Objectives**

The overall objective of this RiskSEARCH sub-study is to understand the participant experience of joining the study and participating, by wearing the Current Health wearable device 24 hours/day and answering daily surveys on the tablet. Research Objectives

1. To explore recruitment and retention for the RiskSEARCH (COVID-19) study
2. To explore feasibility, acceptability, and usability of the intervention, i.e., the Current Health wearable device and tablet
3. To explore barriers and facilitators of study compliance

Interviews with participants and data analysis

We will interview up to 20 participants (depending on data saturation) and ask them to take a modified Telehealth Usability Questionnaire that assesses usability of telehealth implementation and service. (see Appendix C) Participants will be purposively sampled for a range of characteristics (e.g., level of device use, age, gender, socioeconomic status by zip code). We will also specifically seek to interview those who did not take up the intervention to explore the reasons for this. A semi-structured interview guide (Appendix D) will be used to explore participant insights related to acceptability and usability of the website and Current Health device/tablet, patterns of usage, and barriers to use.

Interviews will be completed by trained study team members via telephone or internet-based call. Interviews will be audio recorded and transcribed verbatim with the help of HIPAA-compliant software (e.g., Trint). Participants will have the opportunity to request sole interviewers and handwritten note taking of responses. A separate informed consent process will take place for the qualitative interviews.

Qualitative data analysis will explore the acceptability of the intervention, the extent to which participants engaged with it, and contextual factors that may have influenced engagement. The study team will analyse data using qualitative and quantitative methodologies. Qualitative methods using software (e.g., NVivo) will include analysis to identify emergent themes that could provide direction for future design improvements to make the device more comfortable or engaging. Quantitative methods will include the use of descriptive statistics to report frequencies of responses.

## **Research governance**

### **Ethical issues**

As this study involves human subjects, we will submit an application to the Advarra Institutional Review Board. Participation in this study has a low risk of harms and discomforts: the Current Health device is a widely deployed wearable that has been subjected to rigorous usability testing. Potential participants will be made aware of potential harms and discomforts in the Informed Consent Form. During the consenting process one of our study team members will be available to answer any concerns or questions. Participants will be compensated for their time during the study, contingent on their wearing the device for the duration of the study and completing the daily survey and returning the device at the end. Participants may leave the study at any time. If a participant does experience any adverse event, this will be investigated using the Current Health Post Market Surveillance process.

As with many studies, there is a chance that confidentiality could be compromised; however, we are taking precautions to minimize this risk. All our participant data will be de-identified for analysis.

### **FDA Clearance**

Current Health has 510k FDA regulatory clearance for use in the USA. The clearance covers both the physical wearable and relevant cloud-based software components of the platform for wearable vital signs monitoring and alarming of patients both in the hospital and at home.

The 510k clearance was obtained for Generation 1 (G1) of the wearable device. Participants in the study will be using the newer iteration, Generation 2 (G2). G2 uses the same sensing optics and has an identical technical specification to G1, but is smaller and lighter, improving patient comfort. G2 is being released under the FDA's Enforcement Policy for Non-Invasive Remote Monitoring Devices Used to Support Patient Monitoring During the Coronavirus Disease 2019 (COVID-19) Public Health Emergency (Revised), while formal 510k is concurrently sought. Further information is available in the Current Health Outline Regulatory Strategy (200911) if required.

## **Data Management & Security**

After participants are identified as being eligible for this protocol, they will be assigned a randomized and unique identifier under which all subsequent data will be stored. The only mechanism for linking this number to the participant will be through a key that is stored within the Current Health Firewall. Only study team members will have access to the key. Consequently, all participant data collected by the Current Health Device will be stored under this anonymized number, and any information linking to participant data collected by Current Health study team members will also be anonymized under this number. The key will be destroyed at the end of the data analysis portion of this study. For the qualitative substudy, all de-identified interviews will be recorded and stored on a HIPAA compliant platform until transcribed. Once the data are analyzed, audio recordings will be destroyed.

Participant data (including daily survey data) are sent to the Current Health cloud-based system when participants are near the transmitter located within their homes. De-identified welcome survey data are collected and stored in Jotform's HIPAA compliant database. No Protected Health Information (PHI) data is transmitted via the wearable, only anonymized raw waveform data. The device will not attempt to transmit data under unregistered/free access wifi systems and will store data for up to ten hours in the absence of the home-based hotspot. The servers (SOC-2 certified AWS data centers) and solutions housed by Current Health meet stringent guidelines for HIPAA security. The Current Health Information Security Management System is ISO 27001 certified, and also 21 CFR Part 11 and HIPAA Compliant.

Current Health has robust security standards that meet HIPAA compliance standards and no identified, identifying data, or key will be shared or transferred.

Internally, all data collected, stored or analyzed at Current Health will be done behind the Current Health firewall. As noted above, no data used for analyses will be identifiable other than by the unique, random participant number assigned at the time eligibility is determined. All computing systems and servers at Current Health used for these study data are HIPAA compliant. Shared drives are password protected, backed up daily on secure servers, and ensure version control.

## **Device Decontamination**

Current Health has stringent post-use device reprocessing and decontamination methods for medical facilities using methods that meet or exceed both ISO and FDA guidelines for the decontamination of reusable medical devices. Their pre-existing decontamination strategies have already been shown to be effective at eliminating SARS-CoV-2/COVID-19.

Current Health works with chosen medical logistics partners who are experienced in handling, decontaminating and recycling medical equipment. Each kit is shipped back to Current Health in specific medical bags to ensure safety of courier staff as well as staff employed by their medical logistics partners.

## Timeframe

The award was granted 30 September 2020. Enrollment for the pilot study will begin in January 2021 will be conducted over eight months with a final report submitted in August 2021.

## Dissemination

The primary dissemination method will be the preparation of a report for the Biomedical Advanced Research and Development Authority (BARDA) of the U.S. Department of Health and Human Services. A draft final report will be prepared for BARDA for review and comment and the study team will revise as required for the final report. The final report for this project will provide a comprehensive overview of the work undertaken and results obtained. This will then be prepared for publication in an academic journal.

[figure not shown]

## Appendix A. Simplified Bayesian Network

A simplified Bayesian network. This is an example of a “base model”, where no observations specific to a patient have been specified.

## Appendix B. Sample Size Calculations with Multiple Considerations

**Calculation 1: Sample size required for precise estimation of the overall outcome probability in the target population. In this study a 10% event rate has been estimated. The number of participants required under the assumption this is a true event rate:**

**Binary outcomes:** For a binary outcome, an approximate 95% confidence interval for the overall outcome proportion ( $\phi$ ) is,

$$\hat{\phi} \pm 1.96 \sqrt{\frac{\hat{\phi}(1-\hat{\phi})}{n}}$$

and so the absolute margin of error ( $\delta$ ) is  $1.96 \sqrt{\frac{\hat{\phi}(1-\hat{\phi})}{n}}$ . Thus, to aim for precise estimation of the overall outcome probability in the target population, based on the anticipated outcome proportion ( $\hat{\phi}$ ) and the desired margin of error, the required sample size is calculated as:

$$n = \left( \frac{1.96}{\delta} \right)^2 \hat{\phi}(1-\hat{\phi})$$

To estimate the required number of participants to properly observe 10% event rate at margin error of  $\leq 0.05$ :

$$n = \left( \frac{1.96}{0.05} \right)^2 0.1(1-0.1) = 139 \text{ participants}$$

This calculation does not represent the main goal of the study, rather is the lowest bar for number of participants for the state event observation rate.

**Calculation 2: Sample size required to help ensure a developed prediction model of a binary outcome will have a small mean absolute error in predicted probabilities when applied in other targeted individuals.**

Given that we do not know the predictive power of a model, this estimate is conservative to apply a model to new individuals. The calculation below is given with an event rate of 0.1 (10%) ( $\phi$ ) and approximately 30 model parameters ( $P$ ) based upon our 21 variables listed in the study.

For a binary outcome van Smeden et al use simulation, across a range of scenarios, to derive an approximation (on the natural log scale, denoted by  $\ln$ ) of the expected average error in the outcome probabilities when a derived model is applied to new individuals from the target population. Their derived formula was originally developed based on 12 or fewer predictor parameters, but we have since updated the simulations to allow for 30 or fewer predictor parameters. The derived formula is:

$$\ln(\text{MAPE}) = -0.508 - 0.544\ln(n) + 0.259\ln(\phi) + 0.504\ln(P)$$

Here,  $n$  is the sample size of the development dataset,  $\phi$  is the anticipated outcome proportion ( $\leq 0.5$ ), and  $P$  is the number of candidate predictor parameters ( $\leq 30$ ). MAPE denotes the Mean Absolute Prediction Error (i.e. the average error in the model's estimated outcome probability one would allow for in the intended setting of application of the model). Rearranging this equation, and choosing a target value for MAPE, the required sample size is:

$$n = \exp \left( \frac{-0.508 + 0.259\ln(\phi) + 0.504\ln(P) - \ln(\text{MAPE})}{0.544} \right)$$

$$n = \exp \left( \frac{-0.508 + 0.259\ln(0.1) + 0.504\ln(30) - \ln(0.05)}{0.544} \right) = 756 \text{ participants}$$

## Appendix C. Telehealth Usability Questionnaire

Telehealth Usability Questionnaire								
Components	Question	7	6	5	4	3	2	1
Usefulness								
1	Current Health improves my access to healthcare services							
2	Current Health saves me time traveling to a hospital or specialist clinic							
3	Current Health provides for my healthcare needs							
Ease of Use & Learnability								
1	It was simple to use the Current Health kit							
2	It was easy to learn to use the Current Health kit							
3	I believe I could become productive quickly using the Current Health kit							
Interface Quality								
1	The way I interact with the Current Health kit is pleasant							
2	I like using the Current Health kit							
3	The Current Health kit is simple and easy to understand							
4	This Current Health kit is able to do everything I would want it to be able to do							
Interaction Quality								
1	I could easily talk to the clinician using the Current Health tablet							
2	I could hear the clinician clearly using the Current Health tablet							
3	I felt I was able to express myself effectively							
4	Using the Current Health tablet, I could see the clinician as well as if we met in person							
Reliability								
1	I think the visits provided through Current Health are the same as in-person visits							
2	Whenever I made a mistake using Current Health, I could recover easily and quickly							
3	The Current Health tablet gave error messages that clearly told me how to fix problems							
Satisfaction and Future Use								
1	I feel comfortable communicating with the clinician using the Current Health tablet							
2	Current Health is an acceptable way to receive healthcare services							

3	I would use Current Health services again								
4	Overall, I am satisfied with Current Health								

7: Strongly Agree; 6: Agree; 5: Somewhat Agree; 4: Neutral; 3: Somewhat Disagree; 2: Disagree; 1: Strongly Disagree

\*Adapted from the Telehealth Usability Questionnaire

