2. Increase in pulse rate to more than 90 beats per minute for 60 minutes with minimal body movement (Current Health motion score < 2)
3. Increase in respiratory rate to more than 25 breaths per minute with minimal body movement (Current Health motion score < 2)

In these instances, participants will be contacted and asked the following two to three questions:

We cannot provide you with any medical advice but would like to ask you a few questions. First, have you experienced any new signs or symptoms including:

Shortness of breath  
Chest pain or pressure  
New or worsening cough  
Fever or feeling feverish  
Chills  
Headache  
Sore throat  
Muscle aches or joint pain  
Abdominal pain  
Diarrhea  
Nausea  
Other, please specify

If yes, to any symptom:

- Do you consider the symptom to be mild, moderate, or severe (worst ever)?

- Do you intend to seek medical care at an emergency room, urgent care, or hospital in the near future?
- If no:
- Has your device been working properly, or has it been damaged in any way?

Throughout the study, if a participant believes they have recovered from COVID-19 for any of the reasons listed below and tells the study team they will be resuming normal life and would like to exit the study, we will consider these participants fully compliant. COVID-19 recovery would be considered in any of the following situations:

1. Participant receives a follow-up COVID-19 PCR test that is negative
2. Participant was asymptomatic and isolated for 14 days without symptoms
3. Participant was symptomatic and onset of symptoms was at least 14 days prior with the last three days symptom free

Conversely, if a participant feels that they are experiencing severe symptoms related to SARS-CoV-2/COVID-19 that warrant a visit to the hospital or urgent care facility (which will be also evident by our questionnaire), the participant will be instructed to contact their healthcare provider, contact a nearby hospital to arrange for appropriate assessment, or call 911 if an emergency. We will not provide medical advice, or a real-time monitoring service, as this will likely bias the outcomes of the trial. This will be made explicitly clear to participants in the Informed Consent Form and process of consent. The outcome of that visit will be captured by a study team member.

A study participant will be considered fully adherent to study protocol if they:

- Wear the device for at least 20 hours a day, at least 6 days a week up to 30 days

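### Five of the 21 substudy usability items ask about a clinician or visits that the study does not provide, and four more concern healthcare access or delivery rather than the device and tablet

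*Combined protocol and SAP*

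**What the plan says.** The Protocol's Substudy section lists among its objectives "To explore feasibility, acceptability, and usability of the intervention, i.e., the Current Health wearable device and tablet". Up to 20 interviewees also complete a "modified Telehealth Usability Questionnaire that assesses usability of telehealth implementation and service". The analysis is descriptive: "Quantitative methods will include the use of descriptive statistics to report frequencies of responses". No subscale or total score is defined.

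Appendix C gives the 21 items, each rated from 7 (strongly agree) to 1 (strongly disagree). It offers no not-applicable answer. The items include "I could easily talk to the clinician using the Current Health tablet" and "I think the visits provided through Current Health are the same as in-person visits".

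The Study Design section describes a participant who wears the device and answers a welcome survey and daily surveys on the tablet. It states: "We will not provide medical advice, or a real-time monitoring service". Vital-sign triggers lead to a contact whose purpose is to collect study information, and its script opens by saying that medical advice cannot be given.

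**The concern.** The questionnaire was written for a telehealth service in which patients meet clinicians remotely. The adaptation put the sponsor's product names into the items but kept content that assumes such a service. Someone who never met a clinician through the kit has no experience to report on whether the clinician could be heard or seen.

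Such a respondent might choose the neutral midpoint, disagree, or leave the item blank, and the resulting table could not tell these apart from a real opinion. A low rating for hearing the clinician could be taken as a fault of the tablet when that function was never part of the study. With 20 respondents, each answer moves a frequency by 1/20 = 5 percentage points, so a few such answers would be visible.

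**Working it through.** The plan gives no item count or score to reproduce. The check is a count of the Appendix C items against what the Study Design section says participants receive.

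**Step 1. Classify the items.**

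| Component | Items | Name a clinician or visits | Concern healthcare access or delivery | Remaining |
|---|---|---|---|---|
| Usefulness | 3 | 0 | 3 (items 1, 2, 3) | 0 |
| Ease of Use & Learnability | 3 | 0 | 0 | 3 |
| Interface Quality | 4 | 0 | 0 | 4 |
| Interaction Quality | 4 | 3 (items 1, 2, 4) | 0 | 1 |
| Reliability | 3 | 1 (item 1) | 0 | 2 |
| Satisfaction and Future Use | 4 | 1 (item 1) | 1 (item 2) | 2 |
| Total | 21 | 5 | 4 | 12 |

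**Step 2. Shares.**

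- Items that name a clinician or visits: 5/21 = 24%.
- Those plus the healthcare items: (5 + 4)/21 = 9/21 = 43%.
- Items in neither group: 21 − 9 = 12. These include all 3 + 4 = 7 items on ease of use and interface quality.

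**Step 3. Does any study contact supply what the five items assume?**

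- Consent conversation (Recruitment Strategies): with a study team member, by telephone or Zoom, before the kit is shipped. It is not held on the study tablet.
- Trigger contact (Study Design): for data capture, with medical advice expressly ruled out. It is not described as a clinician visit or as taking place on the tablet.
- Daily tablet use (Study Design): reminders and survey answers only.

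None of these is a clinician encounter through the kit, and no other section describes one.

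**Step 4. Sensitivity to borderline items.** Interaction Quality item 3, on being able to express oneself, names no clinician and could be answered about surveys or staff calls. Satisfaction item 3, on using the services again, is also ambiguous. Adding the first gives 10/21 = 48%, and adding both gives 11/21 = 52%. Neither is counted here because its wording does not require a clinician or care.

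**The case against.** The strongest reply is that the four healthcare items are not defective in the way the five are. They are attitude statements. A participant who was told that no care is given can meaningfully disagree that the product meets their healthcare needs, and that answer bears on acceptability, which is a stated aim. The substudy also describes the instrument as assessing a telehealth service, which is wider than device ergonomics. This stands. It is why the four are counted separately and why deleting them is not required.

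A second reply concerns compulsion. A reader might infer that respondents are forced to rate something that did not happen. The documents do not say so. The Appendix D script lets interviewees decline any question, and SAP section 10 bases percentages on non-missing data, so blanks would drop out if that convention were applied here. Even so, the Appendix D script is written for the interview, SAP section 10 does not mention the substudy, and a blank does not show whether an item was inapplicable or merely skipped.

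A third reply is that the damage is contained. Only item frequencies are planned, so an inapplicable item on its own line cannot distort the others, and many readers would see from the wording that it concerns a clinician. Appendix D also asks directly about set-up, technical problems, comfort and tablet use. This stands too and limits the importance of the point.

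None of these replies rescues the five explicit items. No text in the protocol or SAP supplies the clinician contact or visits they ask about.

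**Conclusion.** The point holds for five of the 21 items (24%), whose frequencies would be uninterpretable as planned. Four more items do not directly measure usability of the device and tablet, giving 9 of 21 (43%), but they can still be read as perceived usefulness or acceptability.

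Two stronger readings are tempting and are not supported. One is that about half the questionnaire is unusable. That requires treating the four attitude items, and at least one item that names no clinician, as equivalent to the five explicit ones. The other is that the questionnaire as a whole, or the study's results, are compromised. Twelve items remain, no composite score is planned, the interview guide covers the kit separately, and the primary and secondary outcomes do not depend on this form.

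The conclusion assumes that Appendix C is the form as it will be administered and that participants have no clinician contact through the kit beyond what the protocol describes. Importance is low.

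**What to change.** - Delete Interaction Quality items 1, 2 and 4, Reliability item 1 and Satisfaction item 1, or reword them to refer to the device, the tablet, the daily survey or calls with the study team.
- For Usefulness items 1 to 3 and Satisfaction item 2, add a not-applicable option, or keep them as they are and report them separately as perceived usefulness or acceptability.
- State in the Substudy section that not-applicable answers are excluded from the frequency denominators, and report their number for each item.

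If the five are deleted, 21 − 5 = 16 items remain. The cost is a small edit to the form and notification of the ethics board. Comparability with the original instrument falls slightly, but this version is already modified and no total score is planned.
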